9.7. Study Product Handling and Disposal

Instructions for study product handling and disposal are provided in the Pharmacy Manual.

10. STUDY PROCEDURES AND ASSESSMENTS

Prior to performing any study procedure and/or assessment (ie, that which is not part of the subject's usual medical care), the Investigator or her/his designee must ensure that the subject or her/his parent/legal guardian has provided informed consent (and/or assent, when applicable) according to the procedure described in [Section 13.5](#), and that the consent has not been withdrawn.

10.1. Study Schedule

The complete study schedule including all procedures and assessments is located in [Section 17.1](#).

10.2. Descriptions of Study Procedures and Assessments

10.2.1. Review of Eligibility Criteria

A review of all eligibility criteria for entry into the study will be performed in association with Visit 1 (ie, during Period 1) to ensure that subjects fulfill all inclusion criteria and do not meet any exclusion criteria (see [Section 7.1](#) and [Section 7.2](#)).

A review of criteria for randomization will be performed in association with Visit 2 to ensure that only subjects fulfilling all of these criteria are randomized ([Section 6.2.2.2](#)).

10.2.2. Demographic Information

Demographic information (age, gender, race, ethnicity) will be collected in association with Visit 1.

10.2.3. Medical History

A complete medical history and review of systems will be performed in association with Visit 1. The medical history should capture all relevant surgeries and procedures as determined by the Investigator.

10.2.4. Vital Signs

Vital signs (supine blood pressure, heart rate, respiratory rate, and oral temperature) will be determined in association with Visits 1, 2, 3, 4, and any unscheduled visits. Vital signs will be determined once per visit for this study.

10.2.5. Weight and Height

Total body weight and height of subjects will be measured in association with Visits 1 and 4.

10.2.6. Targeted Physical Examination

A single targeted physical examination will be conducted in association with Visits 1, 2, 4, and any unscheduled visits. During Period 3, a targeted physical examination will be conducted prior to the first dose of randomized, blinded study product and again on the last day of activities in Period 3 (including the day of early withdrawal, if applicable).

10.2.7. Tanner Staging

Tanner staging will be performed to assess physical development, if appropriate, in association with Visit 1.

10.2.8. Electrocardiogram

A 12-lead electrocardiogram (ECG) will be performed during Visit 1. If serum potassium is < 3.0 mEq/L in association with an unscheduled visit, a 12-lead ECG will be performed.

10.2.9. Cardiac Monitoring

Subjects will undergo cardiac monitoring (eg, Holter monitoring, cardiac telemetry, or other appropriate method). Monitoring will begin prior to the first dose of study product in Period 3 and continue as needed throughout Period 3, including during Visit 4.

10.2.10. Renal Ultrasound

A renal ultrasound will be performed in association with Visit 1 (ie, during Period 1). This must be completed and results assessed before open-label ADV7103 is dispensed to the subject.

10.2.11. Laboratory Assessments

10.2.11.1. Hematology

A complete blood count with differential and platelets will be obtained in association with Visit 1 and prior to the first dose of blinded study product in Period 3. These samples will be analyzed and reported by the central laboratory (ACM Global Laboratories).

10.2.11.2. Serum Chemistry

A serum chemistry panel will be obtained in association with Visit 1. During Period 3, a serum chemistry panel will be obtained prior to the first dose of blinded study product and on the last day of Period 3. In the event of early study withdrawal by a subject following at least 4 weeks of study participation, a serum chemistry panel will be obtained in association with the Early Withdrawal Visit.

The serum chemistry panel will include the following analytes (at a minimum): sodium, potassium, chloride, bicarbonate/total carbon dioxide, blood urea nitrogen, serum creatinine, glucose, calculated eGFR, aspartate transaminase, alanine transaminase, total bilirubin, alkaline phosphatase, calcium, phosphorus, magnesium, and uric acid. These samples will be analyzed and reported by the central laboratory (ACM Global Laboratories).

10.2.11.3. Spot Urine Collection

A spot urine sample will be collected once in association with Visit 1 and twice during Period 3.

During Period 3, the first of 2 urine sample will be collected during the second void of the day (Day 1 of Period 3). This second void of the day follows the first study product dose of the day (morning dose); the first void of the day (not collected) precedes the first study product dose of the day. The second urine sample will be collected on Day 2 of Period 3, within 30 minutes prior to the second study product dose of the day (evening dose).

The urine sample collected during Visit 1 and one of the 2 urine samples during Period 3 will be used for microscopic analysis and dipstick measurement of pH.

Both urine samples collected during Period 3 will be used to provide SS calcium oxalate (CaOx), SS calcium phosphate (CaP), and SS uric acid results. In addition, urinary calcium/creatinine and citrate/creatinine ratios will be provided from these spot urine samples collected during Period 3.

10.2.11.4. 24-hour Urine Preparation/Logistics

Subjects will be given instructions for 24-hour urine collection and, where appropriate, supplies for 24-hour collection. During Visit 2, the investigational site team should confirm that the second 24-hour urine collection was completed and sample sent to Litholink.

10.2.11.5. 24-hour Urine Collection

A 24-hour urine collection will be performed by subjects at home during Period 1 and Period 2 as a remote interaction (with assistance from parents or caregivers, as applicable, during each step of the process). The 24-hour urine collections (a total of 2) will not take place at each remote interaction. Rather, the first of two 24-hour urine collections will take place in association with Visit 1, and the second 24-hour urine collection will be completed during or prior to Visit 2 (ie, via a remote interaction) during the Stabilization Phase of Period 2. In cases where 24-hour urine collections are not feasible, spot urine samples will be requested. All other remote interactions will NOT involve a 24-hour urine collection.

Total urine volume will be recorded, and a well-mixed urine sample will be sent at ambient temperature to Litholink (according to directions from Litholink) or returned to the investigational site. Planned results from these collections include the following: urine volume, SS CaOx, SS CaP, SS uric acid, urine calcium excretion, urine oxalate excretion, urine uric acid excretion, urine citrate excretion, 24-hour urine pH, and potentially others. Spot urine samples may be collected in lieu of 24-hour urine collections in situations when 24-hour urine collection is not feasible.

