As described in [Section 6.2.3](#), the planned duration of stay in Period 3 is 6 days. If required for correction of metabolic acidosis, the duration may be extended beyond 6 days.

The following procedures and assessments will be conducted in association with each subsequent day that a subject remains in Period 3:

- vital signs daily ([Section 10.2.4](#));
- serum bicarbonate and serum potassium ([Section 6.2.3](#) and [Section 10.2.11.6](#));
 - blood samples will be collected every 24 hours after the first dose of blinded study product, unless the Investigator determines that additional sampling is necessary for safe management of the subject.
- spot urine collection ([Section 10.2.11.3](#));
 - The urine sample will be collected during the second void of each day. This second void of each day follows the first study product dose of each day (ie, morning dose); the first void of each day (not collected) precedes the first study product dose of each day.
 - The urine sample collected will be used for microscopic analysis and dipstick testing for determination of pH, as well as to provide SS CaOx, SS CaP, and SS uric acid results.
- concomitant medications ([Section 10.2.13](#));
- adverse events ([Section 10.2.14](#));
- administration of blinded study product ([Section 10.2.18](#)); and
- discharge from Period 3 (on last day).

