12.4. Secondary Analyses

The proportion of subjects with significant hypokalemia up to Day 6 of Period 3 will be similarly analyzed with a CMH test.

The proportion of subjects who fail to maintain serum bicarbonate levels ≥ 18 mEq/L for subjects ≥ 4 years old or ≥ 17 mEq/L for subjects < 4 years old up to Day 6 will be compared

with the CMH test. Time to first episode of metabolic acidosis and time to first episode of hypokalemia will be compared with a log-rank test. Mean change in serum bicarbonate level, mean change in serum potassium level, mean change in urine calcium/creatinine ratio, and mean change in urinary citrate/creatinine ratio will be compared at a last observation carried forward (LOCF) endpoint with an analysis of covariance model, having study product assignment and age category as factors and baseline as a covariate.

Descriptive summaries will be provided by study product and overall for the Open-label Lead-in Period (Period 2).

Safety data will be summarized in the safety analysis set by study product and over time, for each period separately and overall.

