ⁿ Please refer to [Section 10.2.11.3](#) of this protocol for additional important details. During each full day of Period 3, two spot urine samples will be collected. The first of 2 daily urine samples will be collected during the second void of the day. This second void of the day follows the first study product dose of the day (morning dose); the first void of the day (not collected) precedes

the first study product dose of the day. The second daily urine sample will be collected within 30 minutes prior to the second study product dose of the day (evening dose).

^o During Visit 1, subjects will be given instructions for 24-hour urine collection and, where appropriate, supplies for 24-hour collection. During Visit 2, the investigational site team should confirm that the second 24-hour urine collection was completed and sample sent to Litholink.

^p The 24-hour urine collections (a total of 2) will not take place at each remote interaction. Rather, the first of two 24-hour urine collections will take place in association with Visit 1 (ie, following Visit 1 during a remote interaction), and the second 24-hour urine collection will be completed during or prior to Visit 2 (ie, via a remote interaction) during the Stabilization Phase of Period 2. In cases where 24-hour urine collections are not feasible, spot urine samples will be requested. All other remote interactions will NOT involve a 24-hour urine collection.

^q Results to be determined within 2 hours after blood sample collection. During Period 2, blood sample collection should be prior to the morning dose of ADV7103. In the event a blood sample appears hemolyzed to any degree, another sample should be collected as soon as possible for measurement of a serum potassium level. If the degree of hemolysis is severe, another sample should be collected as soon as possible for measurement of a serum bicarbonate level, too.

^r Following first dose of blinded study product. The sampling frequency may be adjusted if the Investigator determines that additional sampling is necessary for safe management of the subject.

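### No urine is collected before the first blinded dose, the urine baseline for the two ratio-change endpoints is undefined, and the Period 3 urine schedules conflict

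*Combined protocol and SAP*

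**What the plan says.** Section 6.3.2 lists mean change in urinary calcium/creatinine and mean change in urinary citrate/creatinine during the Withdrawal Period as secondary endpoints. Section 12.4 compares both at an LOCF endpoint by analysis of covariance, with study product and "age category as factors and baseline as a covariate". Section 12.5 puts secondary efficacy endpoints under sequential gatekeeping.

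Section 10.2.11.3 derives the Period 3 ratios from spot urines: "A spot urine sample will be collected once in association with Visit 1 and twice during Period 3". The first is the second void of Day 1, of which it says: "This second void of the day follows the first study product dose of the day (morning dose". The earlier void is lost: "the first void of the day (not collected) precedes the first study product dose of the day". On the other sample it says: "The second urine sample will be collected on Day 2 of Period 3, within 30 minutes prior to the second study product dose".

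Other current text differs:

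- Section 10.3.3.1 has two samples on the first full day, the later one before that day's evening dose.
- Section 10.3.3.2, for every remaining day, says: "The urine sample will be collected during the second void of each day".
- Footnote n of the study schedule (Section 17.1) says: "During each full day of Period 3, two spot urine samples will be collected". It also sends the reader to Section 10.2.11.3 for details.

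A urine value on stable open-label ADV7103 also exists at Visit 2. Under Section 10.2.11.5 it comes from a 24-hour collection, with a spot sample only where that is not feasible.

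**The concern.** An analysis of change after withdrawal needs a value from before withdrawal, measured in the same way as the follow-up. The protocol does this for blood: Section 6.2.3 completes baseline evaluations before blinded dosing, and Sections 10.2.11.1 and 10.2.11.2 draw hematology and chemistry before the first blinded dose. Urine has no counterpart.

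The analyst must therefore choose between two poor baselines. The Day 1 sample comes after randomization and after a blinded dose of a product whose citrate granules release over 2 to 3 hours (Section 9.1.1). Adjusting for a covariate that treatment may already have moved removes part of the effect. The Visit 2 value precedes treatment but is mostly a 24-hour collection, so it is not like-for-like with a spot void.

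The schedule conflict makes this worse. Sites cannot follow all the passages at once, and the change being estimated differs with the one they follow.

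**Working it through.** The plan gives no figure for these endpoints, so there is none to reproduce.

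**Number of Period 3 samples over six days**

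| Source | Count |
|---|---|
| Section 10.2.11.3 | 2 |
| Sections 10.3.3.1 and 10.3.3.2 | 2 + 5 × 1 = 7 |
| Section 17.1, footnote n | 2 × 6 = 12 at most (the last day may not be a full day) |

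None includes a urine before the first blinded dose. Only Section 10.2.11.3 says that the ratios come from the samples it lists. Sections 10.3.3.1 and 10.3.3.2 name microscopy, pH and supersaturation as the uses of theirs.

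**Timing under Section 10.2.11.3.** Blinded product is given about every 12 hours (Section 10.2.18). With the first blinded dose at 0 h, the Day 2 evening dose is at 3 × 12 = 36 h, so the second sample falls at 35.5 to 36 h. The delay v from first dose to second void is not given. Taking 1 to 4 h:

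- v = 1 h: gap between samples 34.5 to 35 h
- v = 2 h: 33.5 to 34 h
- v = 4 h: 31.5 to 32 h

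By the second sample, three blinded doses have been taken (Day 1 morning, Day 1 evening, Day 2 morning), so a placebo subject has missed three active doses. The corresponding point before the Day 6 evening dose is 5 × 24 + 12 = 132 h. That leaves 132 − 36 = 96 h, or four days, unobserved. If the Day 1 sample is the baseline, LOCF has no intermediate value to carry forward.

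**How much effect is lost.** Suppose the share of the full withdrawal effect reached by time t is f(t) = 1 − exp(−t/τ). The documents give no τ, so 12 to 72 h is an assumption.

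| τ (h) | v (h) | f(v) | f(36) | f(132) | [f(36) − f(v)] / f(36) | f(36) / f(132) | [f(36) − f(v)] / f(132) |
|---|---|---|---|---|---|---|---|
| 12 | 1 | 0.080 | 0.950 | 1.000 | 0.916 | 0.950 | 0.870 |
| 12 | 4 | 0.283 | 0.950 | 1.000 | 0.702 | 0.950 | 0.667 |
| 24 | 2 | 0.080 | 0.777 | 0.996 | 0.897 | 0.780 | 0.700 |
| 48 | 2 | 0.041 | 0.528 | 0.936 | 0.923 | 0.564 | 0.520 |
| 72 | 1 | 0.014 | 0.393 | 0.840 | 0.965 | 0.468 | 0.452 |
| 72 | 4 | 0.054 | 0.393 | 0.840 | 0.863 | 0.468 | 0.404 |

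The post-dose baseline alone keeps a share of 0.702 to 0.965. Stopping at 36 h alone keeps 0.468 to 0.950. Together they leave 0.404 to 0.870. The baseline loss is computed for simple change. An ANCOVA with within-arm slope b subtracts b × f(v), so for b between 0 and 1 its loss from the post-dose baseline is no larger.

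**The daily schedules raise a different problem.** Under Section 6.2.3, subjects with confirmed acidosis return to active ADV7103 and remain monitored for about six days. Section 12.1 assumes this outcome in about 85% of placebo and 15% of ADV7103 subjects by Day 6. Section 12.4 does not restrict the urine LOCF value to blinded product. For much of the placebo arm, the last sample could therefore follow the return to active treatment.

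**The case against.** Three points can fairly be made for the plan.

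- No section calls the Day 1 urine the baseline. A reader might infer that the ANCOVA covariate is post-dose, but the text only leaves it undefined, and the Visit 2 ratio could be meant. This stands. The defect is the missing definition, together with the lack of any like-for-like pre-dose sample to fill it.
- The 36-hour limit belongs to Section 10.2.11.3 alone. Under Section 10.3.3.2 or footnote n there are second-void samples at a matching time of day to the end of Period 3. This also stands, and it makes the conflict part of the problem. It does not restore a pre-dose value, because those samples also begin after the first blinded dose.
- A reader might infer that the endpoints fail to measure withdrawal, or cannot answer their question. The documents do not support that. The arms are randomized and share sampling times, so time of day does not by itself bias the between-arm comparison, and three active doses have been withheld by the Day 2 sample.

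A reader might also infer that urine creatinine goes unmeasured at Visits 1 and 2 because the list of 24-hour results omits it. That list is open-ended, and Section 6.3.2 already requires the creatinine ratios at both visits.

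**Conclusion.** The concern holds for two secondary endpoints. No Period 3 urine precedes blinded dosing, the baseline is undefined, and the sampling passages contradict each other. Those three statements rest on the text alone.

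Under Section 10.2.11.3 the change reflects early, attenuated withdrawal. Within each arm it mixes withdrawal with time of day and time since dose, and about four days go unobserved. The 40% to 87% range is illustrative: it depends on the assumed exponential build-up, τ of 12 to 72 h and a void delay of 1 to 4 h. Because urine not collected before dosing cannot be recovered, this should be settled before further subjects are randomized.

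**What to change.** 1. Collect a spot urine before the first blinded dose on Day 1, and name it in Section 12.4 as the Period 3 urine baseline for both ratios.
2. Bring Sections 10.2.11.3, 10.3.3.1, 10.3.3.2 and footnote n of Section 17.1 to one schedule, with one sample on each later day at the same time relative to dosing as the baseline. Say that the ratios are derived from these samples.
3. Define the ANCOVA/LOCF endpoint as the last such sample taken on blinded product, before any switch to open-label ADV7103.

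If the match is to the morning pre-dose point, the last scheduled sample falls at 5 × 24 = 120 h, compared with about 36 h under Section 10.2.11.3.

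The cost is a wording amendment and about 1 + 5 = 6 samples per subject. That is more than the 2 in Section 10.2.11.3, but no more than the 7 or up to 12 that the other sections already request. Two samples would not be enough, because the last day on blinded product is not known in advance for subjects who switch after acidosis. Those subjects will also have shorter follow-up, probably more often on placebo, and the report should say so when interpreting the result.

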10.2.11.6. Serum Bicarbonate and Serum Potassium

Blood samples will be collected for the measurement of serum bicarbonate and serum potassium levels during Period 2 as specified in [Section 6.2.2](#), with attention paid to proper blood volume limitations for pediatric subjects. During Period 3, samples will be collected pre-dose (AM) for the first 24 hours following administration of the first dose of blinded study product and every 24 hours thereafter unless the Investigator determines that additional sampling is necessary for safe management of the subject ([Section 6.2.3](#)). Blood samples will also be collected for the measurement of serum bicarbonate and serum potassium levels in association with Visit 4.

Samples for measurement of serum bicarbonate will be analyzed within 2 hours after obtaining the sample.

In the event a blood sample appears hemolyzed to any degree, another sample should be collected as soon as possible for measurement of a serum potassium level. If the degree of hemolysis is severe, another sample should be collected as soon as possible for measurement of a serum bicarbonate level, too.

Utilizing whole blood samples (0.1 cc), an electrolyte panel (Cl⁻, K⁺, Na⁺, tCO₂) will be prepared by a qualified delegate/nurse for measure of serum bicarbonate and serum potassium, analyzed and reported at point-of-care via the portable iSTAT System (Abbott Inc.).

